### **Other Functional, Biomarker and Exploratory Outcomes**

A number of additional secondary and exploratory outcomes will be collected and assessed. These objectives include, but are not limited to the following:

- (1) Explore whether greater improvement occurs in additional language, cognitive, adaptive, and behavioral measures in the combination AFQ056/language intervention group relative to the language intervention/placebo group.
- (2) Examine long-term safety and tolerability of AFQ056 in young children with FXS.
- (3) Explore whether improvement can be shown in multiple additional measures from the ERP and eye tracking in the combination AFQ056/language intervention group relative to the language intervention/placebo group.
- (4) Explore whether normalization of eye tracking/pupillometry biomarkers is correlated with improvement in clinical outcome markers including language.
- (5) Explore whether normalization of blood biomarkers of translational pathways regulated by FMRP and mGluR5 receptors is associated with language, functional, and/or biomarker improvements from AFQ056 treatment.
- (6) Explore whether blood levels of AFQ056 correlate with improvement in language, functional, or biomarker measures.
- (7) Explore whether longitudinal analysis shows an improvement in the rate of change of language, functional, or biomarker responses with the language intervention alone, and further improvement in rate of change when AFQ056 is added to the language intervention.

In order to explore these additional objectives, the following outcomes will also be assessed:

- Additional Functional Outcomes
  - Weighted Communication
    - Structured play score
    - Nonstructured play score
  - Preschool Language Scale – 5th Edition (PLS-5)
    - Auditory Comprehension Subscore
    - Total Language Score
  - Mullen Scales of Early Learning (MSEL)
    - Receptive Language Subscore
    - Visual Reception Subscore
    - Gross Motor Subscore
    - Fine Motor Subscore
  - Vineland Adaptive Behavior Scale – Version 3
    - Communication
    - Daily Living Skills
    - Socialization
    - Motor
  - Aberrant Behavior Checklist – Fragile X Validated Version (ABC-FX)
    - Irritability Subscore
    - Stereotyped Behavior Subscore
    - Abnormal Speech Subscore

- Hyperactivity Subscore
  - Social Avoidance Subscore
  - Lethargy Subscore
- Visual Analog Scale (VAS) of Target Behavior (1, 2, & 3 sum)
- Visual Analog Scale (VAS) of Language
- Clinical Global Impression-Improvement (CGI-I)
  - Language
- Clinical Global Impression-Severity (CGI-S)
  - Overall Function
  - Language
- Additional Biomarker Outcomes
  - ERP
    - Auditory Habituation first 15% versus last 15% for amplitude of each of N2 and P2 peaks
    - Resting State – Power in Alpha band, power in Gamma band, and Alpha Reactivity Index (Eyes Open vs. Eyes Closed)
    - Mismatched Negativity Amplitude
  - Pupillometry
    - Maximum Relative Pupillary Diameter Change after each type of emotional stimulus (Calm, Happy, and Fearful)
  - Eye Tracking
    - Percent Looking Time for each of three Individual types of emotional stimulus (Happy, Calm, and Fearful)
    - Number of Fixations for each of three Individual types of emotional stimulus (Happy, Calm, and Fearful)

The Aberrant Behavior Checklist- Community Edition (ABC-C) has been used in virtually all prior trials in FXS to assess maladaptive behavior. This assessment has been validated in populations with intellectual disability and improvements in this scale were used to support FDA approval of Risperdal and Abilify for management of irritable behavior in ASD. The ABC-C was subjected to validation and factor analysis based on over 600 ratings in FXS and found to factor into 6 domains instead of 5. Since that time the ABC using the FX-specific factor analysis (ABC-FX) has been used in FXS trials. The ABC-FX has been sensitive to change in post-hoc subgroup analyses of placebo-controlled phase 2 trials of arbaclofen ([name] 2013) and AFQ056 (Jacquemont 2013) and in the ITT group at the highest dose in a phase 3 trial of arbaclofen.

Visual Analog Scales (VAS) have been used in multiple clinical trials in FXS to measure parent assessment of the level of various problems behaviors or specific functional skills, and the VAS for problem behaviors was sensitive to change in a phase 2 study of arbaclofen in FXS.

Exploratory biomarker outcomes represent key proteins in the signaling pathways regulated by FMRP and thus may normalize with reduction in mGluR5 activity by AFQ056. It is recognized that mGluR5 receptors may not regulate signaling cascades similarly in blood cells and brain, and this is a major reason these measures are considered exploratory. If there were a correlation between one of these markers and clinical response, however, this finding would be extremely helpful to the field, since currently no proven pathway-based cellular or molecular biomarkers of treatment response exist. Hence this trial has included the most promising of the measures that interrogate the mGluR5 pathway being targeted in the trial.

## 9.6 Statistical Analysis Plan

### 9.6.1 Primary Hypothesis

**Primary Efficacy Hypothesis:** *Children treated with AFQ056 will show greater improvement in language and its nonverbal communicative precursors as reflected in on change in a weighted communication score designed to assess both the proclivity to engage in communication and the sophistication of the means employed for communication from baseline (visit 3 assessment) to 8 months (visit 9 assessment) than those treated with placebo.*

The study design is longitudinal involving unequally spaced data collections over the placebo-controlled phase at 0 (baseline), 2, 4, and 8 months (see Figure 2). Focus is on the difference in the rate of change among the placebo (PL) and treatment (TX) groups. To account for the model design and potential dropout, linear mixed models (LMMs) will be used for the analysis.

Suppose that  $Y_{ij}$  is the outcome (e.g., language score) for the  $i^{\text{th}}$  participant ( $i = 1, \dots, N$ ) at the  $j^{\text{th}}$  time point ( $j = 1, \dots, T_i$ ). Assuming linear change over time, the LMM can be written as:

$$Y_{ij} = \beta_0 + \beta_1 t_{ij} + \gamma_0 g_i + \gamma_1 t_{ij} g_i + (b_{0i} + b_{1i} t_{ij} + e_{ij}) \quad (1),$$

where  $g_i = 1$  if the participant is in TX and 0 if in PL,  $t_{ij}$  is time in months,  $b_{0i}$  and  $b_{1i}$  are random effects,  $e_{ij}$  is random error, and the remaining parameters are fixed effects. We make the typical normality and related assumptions for the random effects and random error. Due to randomization, there is no average intercept difference and we set  $\gamma_0 = 0$ . The mean longitudinal change is then: for PL is then:

$$\text{For PL: } E(Y_{ij})_{\text{PL}} = \beta_0 + \beta_1 t_{ij} \quad (1a),$$

$$\text{For TX, } E(Y_{ij})_{\text{TX}} = \beta_0 + (\beta_1 + \gamma_1) t_{ij} \quad (1b).$$

The target of inference is  $\gamma_1$  that represents the mean difference in rate of change among the groups. For the primary language endpoint, treatment efficacy occurs when  $\gamma_1 > 0$ , because language is acquired at a faster rate for TX (cf. Equations 1a and 1b). Therefore, the primary null hypothesis for the analysis is:

$$H_0: \gamma_1 = 0.$$

The LMM is estimated with maximum likelihood, which provides unbiased estimates under an ignorable missing data mechanism. The likelihood ratio test (LRT) will be used to evaluate  $H_0$  by comparing the full model of Equation 1 with a reduced model that omits  $\gamma_1$  (cf. Equations 1a and 1b). There is a one-parameter difference among the models, and the LRT test statistic,  $\chi^2_1$ , has an asymptotic chi-squared distribution. Evidence of treatment efficacy is provided when  $\chi^2_1 > \chi^2_{1,1-\alpha}$ , the latter being the upper  $1 - \alpha$  chi-squared quantile, which leads to the rejection of  $H_0$ . An alternative index of efficacy relevant for this proof-of-concept proposal is the difference in Akaike's information criterion (AIC) among the models. The AIC is an unbiased estimator of  $-2$  times the mean expected log likelihood, and the difference in AIC among two models is their statistical distance. Suppose AIC(full) is the sample AIC for the estimated full model of Equation 1, and AIC(reduced) is that of the reduced model that omits  $\gamma_1$ . Smaller AIC values indicate better statistical fit, so evidence of efficacy is provided when  $\Delta\text{AIC} = \text{AIC}(\text{reduced}) - \text{AIC}(\text{full}) > 0$  because the model with  $\gamma_1 > 0$  has better fit than the model with  $\gamma_1 = 0$ .

AFQ056 for Language Learning in Children with FXS

Version v15

Version date 02/03/2021

The open label phase of the study has both groups receiving treatment (see Figure 2). Change during this phase will also be analyzed using a separate LMM. Focus will again be on the PL and TX slope difference, but the intercept difference will be non-zero ( $\square_0 \neq 0$ ) due to the possibility of a treatment effect in the treatment phase (i.e., an inequality at the end of the treatment phase). The group slope difference might not be statistically significant if the PL group catches up to the TX group during the open label phase. Therefore, the open label phase analysis is considered exploratory.

In the placebo group, LMM analyses will be used to compare trajectory of developmental progress during the 6 months on placebo alone and during the 6 months receiving the language intervention while on placebo. This will generate information about the efficacy of the language intervention alone. Trajectory of developmental progress in these two periods will be compared with trajectory in the 8 months after the placebo group begins AFQ056 in the open label extension.

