**Schedule and Type of Evaluations:** The Language primary outcome assessment (weighted communication scale, WCS) will be obtained at screening, randomization (AFQ baseline), 2 (language intervention baseline), 4, 6, 8, 10, 12, 16 months and post-intervention follow up at 17 months. Cognition, language and behavioral assessments including the, MacArthur Bates Communicative Development Inventory, Preschool Language Scale – 5th Edition (PLS-5), Visual Analog Scale (VAS) of language, Clinician Global Impression-Improvement and Severity (CGI-I, CGI-S) for language and overall function, Mullen Scales of Early Learning (MSEL) Composite and Subscales, Vineland Adaptive Behavior Scale-Version 3 (Vineland-3); Aberrant Behavior Checklist-fragile X validated version (ABC-FX), and a VAS of behavior will be performed regularly throughout the protocol according to the Schedule of Assessments (below, Section 6.1, Table 7) ; Biomarkers including ERP, eye tracking/pupillometry, and blood biomarkers (ERK, AKT, S6 kinase, APP, MMP9, RNA, FMRP, DNA) will also be obtained throughout the protocol according to the Schedule of Assessments. Safety measures will include CBC, CMP, TSH, EKG, adverse events, suicidality.

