At the end of 4 months in the placebo lead-in all subjects will have a repeat battery of assessments and be randomized to drug or placebo at an AFQ baseline visit. The initial dose will be 25 mg BID and dose titration will be done every week based on safety report and side effects alone (efficacy will not be a factor in dose titration due to known strong early placebo effects in prior FXS studies). If the subject has no side effects at each call, the dose will be force titrated (mandatory titration if no side effects) to the next level, 50 mg BID, 75 mg BID and 100 mg BID in order. If there is concern for side effects the dose may be left the same for an additional week or reduced. If there are side effects after the first week of treatment, the 25 mg dose will be allowed to be reduced to 12.5 mg BID. Patients who cannot tolerate 12.5 mg BID will be withdrawn from the study. Subjects will be seen for a study visit for a safety check at 1 month from baseline, during the titration period. The dose can be adjusted weekly through week 7 after baseline. This will give extra weeks after the full titration schedule to ensure the final dose chosen is the optimal one for the given patient. After 7 weeks, the dose will be fixed and at the 2 month visit (language intervention baseline visit) all subjects will have the battery of assessments again and will initiate the language intervention, remaining on a stable AFQ056/placebo dose for the next 6 months.

Families will have training for the language intervention at the 2 month visit, and subsequent instruction and monitoring of delivery of the intervention will occur by weekly video conferencing (per institutional policy) with the language therapist for the first 4 months of the intervention (6 months from randomization), and then monthly for the duration of the study.

Study visits will occur at the 3, 4, 6 and 8 month visits (v6 – 9) after implementation of the language intervention (occurs at 2 months).

- At 3 months: only VAS and CGI assessments will be done
- All baseline assessments except the Mullen, PLS-5, and Children's Sleep Habits Questionnaire will be repeated at 4 and 6 months (visits 7 and 8). Auditory ERP and Eye Tracking will only be repeated at 4 months (visit 7) and not at 6 months (visit 8).
- All baseline assessments will be repeated at the 8 month visit (visit 9), in addition to the EKG and blood/urine tests.

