At all visits, the following will be done: an interim history, vital signs, weight, height, a physical and neurological exam, adverse event review, suicidality review, dosing diary/compliance review, concomitant medication/therapy review, language intervention monitoring/review, and inclusion/exclusion criteria review will be done.

[figure not shown]
- The 8 month (visit 9) assessments will serve to evaluate whether AFQ056 was able to amplify language and communication progress over 6 months in a language intervention.
- The 4 and 6 month (visits 7 and 8) assessments will allow an evaluation of the trajectory over time of effects of the language intervention and any potential additional drug effect and whether it occurs early or there is a progressive building of the effect(s) over time.
- The 4 month assessment will also allow some data to be collected in the case of families who are not able to sustain the language intervention with the same intensity in the later part of the 6 months as opposed to the early months. It is not expected this will be a frequent problem, however.

The 4 month placebo lead-in will allow for placebo effects to stabilize, and for the group ultimately randomized to placebo, there will be 6 months (4 month placebo lead-in + 2 months of placebo dose titration after randomization) of placebo treatment without the language intervention, which will allow this group to serve as a treatment-as usual/medication placebo control group for the 6 month language intervention placebo group, thus allowing the effects of the language intervention alone in FXS to be quantified.

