**Weighted Child Intentional Communication Score (the primary outcome measure)** will be derived from a 22- minute semi-structured examiner/child play session administered at Screening, AFQ Baseline and 2, 4, 6, 8, 10, 12, and 16 month and Follow Up visits (visit 1, 3, 5, 7, 8, 9, 11, 12, 14 and 15). The play session will be administered by designated staff (Speech and Language Pathologists and Psychologists preferred) trained to fidelity on administration of the measure. The sessions involve 12 minutes of structured play prompts designed to elicit a range of communicative behaviors (e.g., requesting, sharing of affect) and 10 minutes of free play with a standard set of toys. The weighted child intentional communication score will be coded from digital videos of the sessions centrally, according to standard coding methods by coders trained to reliability. The weighted communication score reflects child initiated communication that involves the child's use of gestures, eye contact, vocalizations, and/or words and word combinations to communicate a message to a listener. This measure has been shown to grow in a linear fashion across the stages of development that will be displayed by the children enrolled in this study.

Coding of child intentional communication will be based on the occurrence of three classes of behavior:

1. Gestures or nonword vocalizations during which the child coordinated attention between the message recipient and an object or salient event.
2. Conventional gestures (e.g., distal points, head nods, pantomime) with attention to an adult
3. Symbols (i.e., spoken words or signs) that were used in a non-imitative manner.

The Weighted Frequency of Intentional Communication will be obtained by multiplying each intentional communication act by the following weights: nonverbal = 1; single symbol = 2; and multiple symbols = 3. Previous research has indicated that the weighted variable is more sensitive to change over time than the unweighted variable and that growth in the weighted variable (but not the unweighted variable) was related to later level of social impairment in younger siblings of children with ASD and to communication development in FXS. Thus, this measure is objective and expected to be very sensitive to changes in communication ability as the result of the intervention.

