- Longitudinal analysis to determine whether the rate of change in language, functional, or biomarker responses in the group assigned to placebo will be lowest during the first 6 months of the study (Screening to visit 5/month 2), higher in the next 6 months with the language intervention (visit 5/month 2 to visit 9/month 8), and highest in the final 8 months with both the language intervention and AFQ056 treatment (visit 9/month 8 to visit 14/month 16) – with inflection points at visit 5/month 2 when the language intervention is started and visit 9/month 8 when AFQ056 is started.
- Analyses of change from baseline at the 2 month visit (visit 5) will be evaluated for all clinical and biomarker outcomes, to determine if effects of drug alone can be identified before the language intervention is initiated. Likewise analyses of change from baseline and from the final visit before weaning treatment with AFQ056 (16 month visit, visit 14) at the Follow Up visit (visit 15) will be evaluated for all clinical and biomarker outcomes, to determine if regressive effects of coming off drug are evident. Covariates in the analyses will be medication (coded as a factor with a small number of levels), age, and additional variables that are shown to be imbalanced through unlucky randomization.

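### Section 9.6.1 leaves month 6 out of the primary-score visits, and section 9.6 gives no between-arm estimate for months 2–8 to show whether a drug effect arises before or during the language intervention

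*Combined protocol and SAP*

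**What the plan says.** **Visits.** Section 9.6.1 states: "The study design is longitudinal involving unequally spaced data collections over the placebo-controlled phase at 0 (baseline), 2, 4, and 8 months". Other sections schedule the weighted communication score at month 6 as well:

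- The Synopsis schedule of evaluations lists "randomization (AFQ baseline), 2 (language intervention baseline), 4, 6, 8, 10, 12, 16 months".
- Section 6.3.9 says the play session is "administered at Screening, AFQ Baseline and 2, 4, 6, 8, 10, 12, and 16 month and Follow Up visits".
- Section 3 says all baseline assessments except the Mullen, the PLS-5 and the Children's "Sleep Habits Questionnaire will be repeated at 4 and 6 months (visits 7 and 8"). The primary score is not among the exceptions.
- Table 7 in section 6.1 marks it at visit 8 (month 6).

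**Model.** Section 9.6.1 says: "Assuming linear change over time, the LMM can be written as". It then fits one straight line per arm over months 0–8 with a common intercept. The target is γ1, and γ1 > 0 is read as efficacy "because language is acquired at a faster rate for TX". The hypothesis concerns change from visit 3 (month 0) to visit 9 (month 8).

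**Timing.** Drug starts after visit 3 and the language intervention at visit 5 (month 2). Section 3 says the month 4 and month 6 visits will show the trajectory of any drug effect and "whether it occurs early or there is a progressive building of the effect(s) over time". Sections 9.3 and 9.6.3 plan an evaluation of all outcomes at visit 5 to look for an effect of drug alone. Section 9.6.3 also plans a placebo-arm analysis "with inflection points at visit 5/month 2 when the language intervention is started".

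**The concern.** Two separate things look incomplete.

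First, the section that defines the primary analysis disagrees with four other places about which primary data exist. If the printed list were followed literally, one of the four post-baseline primary assessments would go unused.

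Second, drug exposure and the learning intervention start two months apart, and a single slope over months 0–8 averages across both periods. The primary objective treats the gain after six months of intervention as a marker of plasticity, and section 9.1 describes improvement over six months. A positive γ1 is compatible with a benefit that builds during the intervention. It is also compatible with one that is complete by month 2 and then stays level. Section 3 asks which of these occurs, but section 9.6 specifies no between-arm contrast for months 2–8. What is at stake is how a positive result is interpreted, not whether the test is valid.

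**Working it through.** **1. The plan's own figure.** The 50 per arm in section 9.8 cannot be rebuilt, because the variance components, the placebo slope and the visit times used are not given. Its alpha can be checked: ΔAIC > 0 means χ²₁ > 2, and P(χ²₁ > 2) = 0.157, which rounds to the stated 0.16. Moving from alpha 0.10 to 0.16 at 80% power scales N by (1.405 + 0.842)² / (1.645 + 0.842)² = 0.816. That gives 50 × 0.816 = 40.8, against the stated 40 per arm. Nothing below changes these figures.

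**2. Assumed variances.** Because the planners' values are not given, the SDs of the weighted score in the two non-FXS cohorts of section 6.3.9 are used.

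- Cohort A: 10.2 rising to 17.9 over 16 months (months 14 to 30).
- Cohort B: 6.29 rising to 20.50 over 9 months.
- Grid: residual share of starting variance 0.1–0.4, intercept–slope correlation 0–0.4, 50 per arm.

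Example, cohort A, residual share 0.25, correlation 0.2: starting variance 10.2² = 104.04, residual variance 26.01, intercept variance 78.03 (SD 8.833). The slope SD s solves 17.9² = 104.04 + 2(0.2)(8.833)(16)s + 256s², giving s = 0.816 per month.

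**3. Formulas.** Let t be the visit times, V the within-child covariance matrix from the random intercept, random slope and residual, and d the true between-arm difference at each visit. With equal arms and γ0 = 0:

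- E(γ1) = t′V⁻¹d / t′V⁻¹t
- Var(γ1) = (2/n) / t′V⁻¹t

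Only the difference between arms enters, so a bend shared by both arms does not bias γ1. For a knot at month 2, t is replaced by X = [min(t, 2), max(t − 2, 0)], and the covariance is (2/n)(X′V⁻¹X)⁻¹.

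**4. Month 6.** In the example, SE(γ1) is 0.2361 with visits 0, 2, 4, 8 and 0.2281 with month 6 added: 1 − (0.2281/0.2361)² = 6.7% less variance. Over the grid, with complete data, the cut is 3.3–8.7% (A) or 0.3–1.4% (B). As a standard error that is 1.7–4.5% or 0.15–0.7%. With 20% dropout by month 8, spread evenly over the four two-month windows, the variance cut is 4.6–10.1% (A) or 0.5–2.3% (B).

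**5. What γ1 can and cannot separate.** Let D be the true visit-9 difference, with five visits.

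| True shape | 8 × γ1 as share of D, A | B | Knot model, month 2–8 slope difference |
|---|---|---|---|
| All of D present by month 2, level after | 75–95% | 45–95% | 0 |
| Nothing until month 2, then linear | 102–108% | 102–118% | D/6 per month |

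γ1 is positive in both rows. The knot model's slope tells them apart, and its visit-9 difference has expectation D in both.

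**6. Precision of the knot model.**

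| Quantity | A | B |
|---|---|---|
| SE of visit-9 difference, relative to 8 × γ1 | 0.1–1.7% larger | 0–1.2% larger |
| SE of month 2–8 slope difference, relative to γ1 | 12–32% larger | 0.4–4.6% larger |
| 95% half-width, month 2–8 slope (points per month) | 0.38–0.67 | 0.72–0.92 |
| 95% half-width, γ1 (points per month) | 0.34–0.51 | 0.71–0.88 |
| 95% half-width, month-2 difference (points) | 1.7–3.0 | 1.8–2.5 |

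**The case against.** **The visit list may be clerical.** The sentence describes the design generically, the same model is reused for ERP and eye tracking, and months 0, 2, 4 and 8 are exactly when those are collected. The tolerance paragraph of section 9.3 carries a similar 2, 4 and 8 month list. The index Tᵢ in Equation 1 admits any visit. This stands. A reader might infer that month-6 scores will be discarded, but no section says so. What remains is a conflict in the text that should be settled.

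**The plan already checks for an early effect.** Section 9.3 (Number of Arms) evaluates all outcomes, including the primary one, at visit 5, and section 9.6.3 repeats this. These analyses address the very case that makes γ1 ambiguous, and the half-widths above suggest the month-2 difference would be informative. This also stands, and it rules out any claim that the plan ignores the question. Those analyses stop at month 2, however, and do not estimate the between-arm difference in change over months 2–8.

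**The test matches the hypothesis.** The hypothesis runs from visit 3 to visit 9, which is γ1's window. A reader might infer that γ1 is biased or gives false positives when the benefit comes early. It does not: an early benefit is a real drug effect. It is also an extreme shape, since section 2.1 expects learning effects to be measurable only over time. The sentence about a faster rate correctly explains γ1 > 0 under Equation 1 and is not an error.

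**Detail may sit elsewhere.** Section 9 promises a formal statistical analysis plan. The added model could be specified there, but the visit list in 9.6.1 should still be corrected.

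**Conclusion.** Both parts hold in limited form, and the severity is minor.

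The month-6 omission is a direct inconsistency with the Synopsis, section 3, Table 7 and section 6.3.9. Settling it brings a modest precision gain and no bias in either direction.

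The second part is a limit on interpretation. γ1 can establish greater improvement over months 0–8. It cannot alone place that improvement before or during the intervention, and the question raised in section 3 has only its month-2 half covered by a planned between-arm analysis.

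The percentages rest on variances from non-FXS cohorts and on an assumed residual share and correlation. The spread between cohorts A and B shows how far they could move in this trial. Two findings do not depend on those values: the visit lists disagree, and the single slope does not by itself identify when an effect arose.

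**What to change.** 1. In section 9.6.1, state that the primary score is analysed at months 0, 2, 4, 6 and 8. Remove the description of the visits as unequally spaced for this outcome, because those five visits are evenly spaced. The 0, 2, 4, 8 list can be kept for ERP and eye tracking.

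2. Keep the γ1 test as the primary analysis, unchanged. In reporting, describe a positive γ1 as greater improvement over months 0–8.

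3. Add one supporting, estimation-only model with a knot at month 2 in time and in time × group. Report its month-2 difference, month 2–8 slope difference and visit-9 difference with 95% confidence intervals beside γ1. Cross-reference the visit-5 analyses in sections 9.3 and 9.6.3.

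4. Put no significance gate on the supporting model. Its month 2–8 slope is less precise than γ1, so its interval can include zero when γ1 is clearly positive.

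The cost is a corrected list and one extra model on data already collected.
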